1.0 OBJECTIVES

Breast cancer is the most common cancer for women in the U. S. and an estimated 232,340 women will be diagnosed in 2013.¹ After diagnosis, women and their physicians must consider many treatment-related decisions which are often made quickly while women are still adjusting to the news of their diagnosis. For women with unilateral breast cancer, another option is the removal of the cancer-free breast (contralateral prophylactic mastectomy, CPM). In our research, more than 59% of women with breast cancer have initial interest in CPM; thus, this is an issue that affects the majority of women with breast cancer. The use of CPM in patients with sporadic unilateral invasive breast cancer increased by 150% from 1993 to 2003 and its use continues to increase.^{2,3} While CPM reduces the risk of developing a contralateral breast cancer, there is no evidence that it reduces breast cancer mortality or overall death.⁴ Women with early stage sporadic breast cancer have a 0.5 to 0.75% annual risk of developing contralateral breast cancer⁵⁻⁸ and for most, the risk of distant metastatic disease is greater than the risk of developing a contralateral breast cancer. Despite evidence that adjuvant endocrine therapy reduces the risk of contralateral breast cancer,⁹⁻¹¹ an increasing number of women choose CPM; however, the outcomes of these patients are not well understood. Much of our knowledge about prophylactic mastectomy is from studies of high risk women who have a 40-65% lifetime risk of developing breast cancer^{12,13} and represent less than 10% of breast cancer patients. Thus, little information is available to help average risk women make this important and irreversible healthcare decision. This study will provide the data critical to inform women about the likely psychosocial outcomes if they undergo CPM or receive standard of care (no CPM). We expect the results will improve patients' understanding of the benefits and risks of CPM and guide the development of evidence-based practices to enhance the individualized treatment decision-making process.

Specific aim is to:

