- 1) To prospectively examine the psychosocial outcomes of women with sporadic breast cancer who have CPM versus those who do not. We will also determine the impact of patient and physician characteristics on the outcomes. We hypothesize that women who have CPM will have more decisional regret (the primary outcome), cancer-specific distress, cancer worry, and fear of recurrence and lower satisfaction with their decision than those who do not have CPM.

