2.0 BACKGROUND AND RATIONALE

Breast cancer is the leading cause of cancer among women in the U.S., affecting approximately 226,870 women annually.¹⁴ The majority of patients (93%) are diagnosed with operable disease and undergo surgical management of the affected breast with either breast conserving surgery or mastectomy.¹⁵ It is well recognized that adjuvant systemic chemotherapy has substantially reduced the probability of dying from breast cancer.¹⁶ Among women with hormone-positive breast cancers, adjuvant treatment with tamoxifen or aromatase inhibitors reduces the risk of developing a contralateral breast cancer by

approximately 50%.⁹ In fact, it is estimated that the combination of mammography screening and adjuvant systemic therapies have contributed to a 30% overall reduction in breast cancer mortality over the past decade.¹⁷

Despite these major achievements over the past two decades in reducing breast cancer mortality through evidence-based practices, there has been a rising incidence of CPM. The combined annual rate of CPM (~8%) in population-based studies of women with invasive breast cancer or ductal carcinoma in situ^{2,3} translates into over 18,000 potentially over-treated patients based on an expected 226,870 new breast cancer cases in 2013.¹⁴ Rates of CPM are even higher in academic medical centers and were estimated to be between 14-28% from 2006 to 2007.¹⁸⁻²⁰ These higher than average annual rates of CPM at centers that offer multidisciplinary care may reflect an increasing trend in the numbers of patients with sporadic breast cancer electing to undergo CPM and the availability of plastic surgery expertise for reconstruction. Our previous studies with breast cancer patients suggest that, before meeting with their surgeon, 59% of women indicated they had at least some interest in CPM. Hawley et al. reported in a population-based survey of women from Detroit and Los Angeles that among women undergoing a mastectomy of their affected breast, 53% said that they considered CPM.²¹ Thus, the topic of this proposal affects the majority of women with stage I-III breast cancer.

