Study Measures. The domains chosen for study measures are based on the Integrated Model of Behavior^{45,46} and Ottawa Decision Framework⁴⁷ as well as results of our R21 study of decision-making and CPM.

Background Information. Participant will complete demographic information (i.e., age, race, ethnicity, marital status, education, and occupation). Medical variables (i.e., date of breast cancer diagnosis, method of detection, tumor histology, nuclear grade, stage, human epidermal growth factor receptor (HER2/neu), estrogen receptor (ER) and progesterone receptor (PR) status, and weight and height at diagnosis) will be extracted from patients' charts.

Cancer-Specific Distress. Cancer-specific distress will be measured with the Revised Impact of Events Scale (IES). The IES assesses two common categories of responses to stressful events: intrusion and avoidance. The IES has good internal consistency reliability (0.70 to 0.85).⁴⁸ For this study, patients will be asked to rate the frequency of intrusive thoughts and avoidance behaviors related to their cancer.^{48,49}

Breast Cancer Worry Scale. Breast cancer worry will be assessed with a 4-item scale developed by Lerman et al.^{49,50} These items assess the extent to which worry about breast cancer interferes with women's daily functioning.

Fear of Cancer Recurrence. Fear of recurrence will be assessed with a 5-item scale that measures patients' beliefs and anxieties about disease recurrence.^{51,52} It has been used with a variety of cancer populations and the psychometric properties of this measure have been well-established.^{53,54}

Satisfaction with Decision Scale. A measure of women's satisfaction with their surgery decision.⁵⁵ It has been used with a variety of healthcare decisions

and has been shown to have good reliability and validity.⁵⁵ It will be administered at 1, 6, 12 and 18 months post-surgery.

Decisional Regret. This brief scale measures distress or remorse about the surgical decision.⁵⁶ It has been used to assess regret with a variety of healthcare decisions and has been shown to be reliable and valid.⁵⁶ It will be administered at 1,6,12 and 18 month assessments.

4.0 Statistical Considerations.

Analytic Methods:

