General: Our first steps will be to summarize patients' baseline demographic, risk behavior, and disease-related information using descriptive statistics. This will include means, standard deviations, medians and ranges for continuous variables and frequencies and percentages for categorical responses. Descriptive statistics will be summarized separately for each group and for each group over time for psychosocial variables.

Groups of women will include women who have had CPM and those who have not had CPM. For women for whom we have information on their initial interest in CPM, the latter category of women also being categorized by those who initially had an interest in CPM versus those who did not have an interest in CPM. We will compare information about these groups of women for continuous variables using t-tests, analyses of variance (or their nonparametric equivalents such as Wilcoxon rank sum tests) or for categorical variables chi-square tests or Fisher's Exact tests. Group comparisons tested for significance will include the two primary groups of CPM versus no CPM and also for the women for whom we have information on their initial interest in CPM, the three following groups: initial interest and had CPM, initial interest but did not have CPM, and no interest and did not have CPM.

Our initial primary analyses for each psychosocial variable will evaluate women's psychosocial outcomes over time using a general linear model (PROC GLM in Statistical Analysis Software (SAS)) incorporating information over time (baseline and 1, 6, 12, and 18 months post-surgery) with the psychosocial variable being the dependent variable and whether or not the women had CPM the independent variable. We will determine if the psychosocial variable (on average) differs between the groups, if there are differences over time (averaged over groups), and whether or not these differences of time are different for different groups (a group by time interaction). Analyses will be made in SAS version 9.3 (SAS Institute Inc., Cary, NC, USA).

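### Women choose CPM, but the primary over-time model has CPM status as its only independent variable, and no analysis specifies adjustment for prior differences

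*Combined protocol and SAP*

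**What the plan says.** CPM is not assigned. Section 3.0 (Study Population) expects a minority of women to choose it, and section 4.0 (Sample size) plans on 11.5%, or 32 women against 248.

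**Models.** Section 4.0 (General) describes the initial primary analyses as a general linear model over time, "with the psychosocial variable being the dependent variable and whether or not the women had CPM the independent variable". It tests whether "the psychosocial variable (on average) differs between the groups", whether there is change over time, and whether that change differs by group. Sample size then says that a linear mixed model will be used, and describes it by treatment, time and within-subject correlation. Neither text names a covariate, a stratification or a propensity method.

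**Text that points towards adjustment.** The specific aim adds: "We will also determine the impact of patient and physician characteristics on the outcomes". Missing Data refers to covariates in the model, but only as a condition for unbiased estimates, and lists none. General also compares three groups, "initial interest and had CPM, initial interest but did not have CPM, and no interest and did not have CPM", among women whose initial interest is known.

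**Outcome timing.** The aim states: "We hypothesize that women who have CPM will have more decisional regret (the primary outcome". Of the regret scale, section 3.0 says: "It will be administered at 1,6,12 and 18 month assessments". Satisfaction with the decision has the same schedule. General and Sample size nevertheless list a baseline visit for the outcomes without exception.

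**Use of the result.** Section 1.0 says the data will inform women about likely outcomes "if they undergo CPM or receive standard of care (no CPM".

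**The concern.** When patients select their own exposure, a two-group contrast mixes any effect of the procedure with whatever distinguishes the women who choose it. The protocol gives its own reasons to expect such differences. Section 2.0 lists age, race and marital status among the influences on surgical decisions. It also links anxiety and worry with management decisions, although in women at high genetic risk. Section 3.0 collects age, race, marital status and stage, and schedules a baseline questionnaire, so adjustment is feasible.

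Regret and satisfaction are the most exposed outcomes. With a pre-decision score, a difference already present could be seen and allowed for. With the first measurement at 1 month after surgery, a prior difference in disposition and an effect of CPM look alike, and the group-by-time term cannot tell them apart. For distress, worry and fear of recurrence the problem takes another form: the averaged group effect counts the baseline visit as a response, so part of the tested difference may precede surgery.

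At stake is whether the regret contrast can be used as section 1.0 intends, to tell a woman what to expect under either choice.

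**Working it through.** **1. The plan's own figure.** Inputs from section 4.0 (Sample size): 32 vs 248, two-sided alpha 0.05, effect 0.54 SD. The standard error in SD units is sqrt(1/32 + 1/248) = 0.188. A two-sample t-test has 81.7% power at 0.54 and 80% power at 0.528, so the stated 80% is reproduced. That calculation assumes an unconfounded difference.

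**2. What each text specifies.**

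| Place | Bearing on adjustment |
|---|---|
| 1.0, specific aim | patient and physician characteristics; no model, no list |
| 4.0, General, over-time model | CPM status, time, group by time |
| 4.0, General, three groups | initial interest; t-tests or analysis of variance, not a term in the over-time model |
| 4.0, Missing Data | covariates mentioned, none named |
| 4.0, Sample size, mixed model | treatment and time only |

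**3. Reach of the initial-interest comparison.** Interest is asked only of women seen at the initial surgical consult. There is no group for women without initial interest who had CPM. Section 2.0 reports that "59% of women indicated they had at least some interest in CPM". If that share applies to all 280, all were screened, and every CPM woman had interest (assumptions), then 0.59 x 280 - 32 = 133.2 interested women did not have CPM. For 32 vs 133 the detectable effect is 0.555 SD, with 77.8% power at 0.54. If half were screened (assumption), 16 vs 66.6 detects 0.789 SD, with 48.3% power at 0.54.

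**4. Illustration of bias, partly anchored in the documents.** Interest among women without CPM is 133.2/248 = 53.7% if all CPM women were interested, a gap of 0.463. If 80% of CPM women were interested (assumption), it is (165.2 - 25.6)/248 = 56.3%, a gap of 0.237. Suppose interested women differ by 0.2 to 0.5 SD on the outcome (assumption):

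- Shift: 0.237 x 0.2 = 0.047 SD to 0.463 x 0.5 = 0.231 SD.
- Rejection at 18 months with no effect of CPM: 5.7% to 23.3%.

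**5. Illustration resting wholly on assumptions.** A prior trait is imbalanced by 0.2 to 0.5 SD and correlates 0.3 to 0.5 with the outcome:

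- Shift: 0.2 x 0.3 = 0.06 SD to 0.5 x 0.5 = 0.25 SD.
- Rejection at 18 months: 6.2% to 26.4%.
- Rejection for the four-visit mean, variance factor (1 + 3r)/4, at r = 0.5: 6.9% to 38.9%.

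**6. Precision after adjustment.** Detectable effect = 0.528 x sqrt((1 - R2 outcome)/(1 - R2 CPM)). With outcome R2 of 0 and CPM R2 of 0.1, 0.2 and 0.3 (assumptions), it is 0.557, 0.590 and 0.631 SD, and power at 0.54 is 77.6%, 72.7% and 66.9%. It falls below 0.528 only if the covariates explain more of the outcome than of CPM choice.

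**7. Risk from a late baseline.** If the decision itself moved distress and worry by 0.1 to 0.3 SD before baseline was taken, and their association with the outcome is 0.5 (assumptions), adjusting for them adds 0.5 x 0.1 = 0.05 to 0.5 x 0.3 = 0.15 SD of bias. Section 3.0 places baseline only around enrollment.

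**The case against.** The best defence is that adjustment is signalled. The over-time model is called an initial analysis, the aim promises to study patient and physician characteristics, and Missing Data assumes covariates in the model. An unadjusted first step followed by covariate models fits this text. The Sample size paragraphs are mainly a power calculation, simplified by their own account, so a missing covariate list there is weak evidence. The only table is numbered 3 and no physician measures are listed, which suggests an abridged text, although that is an inference. The aim is also worded as a comparison: taken purely as an association, an unadjusted difference is not a test error.

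Much of this stands. A reader might infer that the plan rules out adjustment. The documents do not support that; they show adjustment hinted at and left unspecified. A reader might also infer that a regret baseline was wrongly omitted. It was not: regret about a decision cannot exist before the decision.

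The defence does not remove the point. No analysis turns the hints into a model, and covariates chosen after the results are seen would be less credible. The initial-interest comparison is a real safeguard, but it covers only part of the sample and sits outside the over-time model. The use stated in section 1.0 goes beyond description.

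**Conclusion.** The concern holds as one of unspecified adjustment in a self-selected comparison. As written, the regret contrast cannot distinguish an effect of CPM from prior differences between women who choose it and women who do not.

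Its size and direction are unknown. The documents give no association between any confounder and regret, so the shifts and rejection rates above are illustrations. At the low end the rejection rate barely leaves 5%. A reader might infer that the plan's false-positive rate is 23% or 26%, or that the bias favours the stated hypothesis. Neither follows from the documents.

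Separately, the baseline visit listed for the outcomes in section 4.0 conflicts with the regret and satisfaction schedules in section 3.0. These passages must be reconciled.

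**What to change.** 1. **Check timing first.** Compare baseline dates with surgery and, where possible, with the CPM decision.
2. **Primary contrast.** Use a linear mixed model of the 1, 6, 12 and 18 month visits, with all women without CPM as the comparator. Adjust for a short prespecified set of clearly pre-decision variables already collected, for example age, race, marital status, stage (as known before surgery) and site. With about 32 CPM women, a propensity score built from these is an alternative.
3. **Baseline distress and worry.** Add them to the primary model only if baseline precedes the decision. Otherwise use them in a sensitivity analysis restricted to women in whom it does.
4. **Distress, worry and fear as outcomes.** On the same condition, use the outcome's own baseline as a covariate, not as a response.
5. **Initial interest.** Add it as a covariate in a supporting model among screened women, keeping those without initial interest who had CPM.
6. **Text and reporting.** Correct the visit list in section 4.0 for regret and satisfaction, report the unadjusted model alongside, and describe results as associations.

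The cost is SAP wording and a check of dates. The downside is the possible loss of precision in step 6 of the working. For the four-visit mean the detectable effect would be 0.364/sqrt(0.9) = 0.38 SD (r = 0.3, CPM R2 0.1) to 0.465/sqrt(0.7) = 0.56 SD (r = 0.7, CPM R2 0.3), where 0.364 and 0.465 are 0.528 x sqrt((1 + 3r)/4). Adjustment deals only with what is measured; unmeasured confounding remains.

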Missing Data. Because we are using patient-reported outcomes, some individuals will fail to complete all questionnaires. PROC GLM in SAS is designed to handle this type of missing data and will give unbiased estimates of effects over time provided that the probability of having missing data depends only on the covariates in the model. We will check this assumption by looking at predictors of missing data. We will also run analyses to examine whether study participants who drop out of the study early differ from those who do not. With the use of PROC GLM, we will be able to include all participants in the analysis, even those with missing values for some time points and those who drop out early. We will also use alternative multiple imputation methods to estimate missing values using differing assumptions if the data appear to not be missing at random. Several

strategies will be used to decrease the chance of missing data and non-compliance. Forms will be reviewed upon receipt to ensure all items are completed, and if incomplete, participants will be contacted to determine if the question was deliberately skipped and, if not, to get a response. Patients will be contacted numerous times by mail and by phone to ensure questionnaire completion. Scheduling of follow-up visits will coincide with clinic visits, and as such, missing data will be kept at a minimum.

Sample size: Given information from the recently completed R21 study and rates over the past 5 years, we estimate that approximately 11.5% of women meeting eligibility criteria will have CPM. All power analyses assume a significance level of 0.05 and a two-sided test. Assuming a 10% attrition rate and an additional loss of 10% of patients due to eligibility changes post-enrollment, we will enroll approximately 345 participants to ensure that approximately 311 participants continue on study to yield complete data on at least 280 participants. Therefore, about 32 women will have CPM, and 248 will not. For comparisons of these two groups of women, a sample size of 280 (32 in the CPM group and 248 in the non CPM group) at 18 months post-surgery will provide 80% power to detect an effect size of 0.54 or greater for the continuous dependent variables.

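### Section 4.0 names both PROC GLM and a linear mixed model for the primary outcome, and PROC GLM as specified cannot both keep every woman and give a valid CPM test

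*Combined protocol and SAP*

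**What the plan says.** The specific aim in section 1.0 hypothesises that "women who have CPM will have more decisional regret (the primary outcome").

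Section 4.0, General, sets the primary longitudinal analysis of each psychosocial variable, "using a general linear model (PROC GLM in Statistical Analysis Software (SAS)) incorporating information over time", "with the psychosocial variable being the dependent variable and whether or not the women had CPM the independent variable". It will test the average group difference, change over time, and "whether or not these differences of time are different for different groups (a group by time interaction"). No subject term, REPEATED or RANDOM statement, or covariance structure is given.

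Section 4.0, Missing Data, rests on the same procedure: "With the use of PROC GLM, we will be able to include all participants in the analysis, even those with missing values" at some visits or early dropout. Estimates are said to be unbiased "provided that the probability of having missing data depends only on the covariates in the model". The plan adds: "We will check this assumption by looking at predictors of missing data". Multiple imputation is held back, to be used "using differing assumptions if the data appear to not be missing at random".

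The text leading to Table 3 says that the primary psychosocial outcomes are correlated within subjects, so a linear mixed model will be used. Table 3 is built on that model with correlations of 0.3, 0.5 and 0.7.

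Section 3.0 schedules decisional regret and satisfaction with decision at 1, 6, 12 and 18 months only, with no baseline measurement.

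**The concern.** Two different analyses are named for the primary outcome, with no order of precedence. The one called primary is credited with a property it does not have in the form described. PROC GLM can be run on these data in two standard ways:

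- **One row per woman, with REPEATED.** The error term for CPM is between women, which is sound, but any woman with a missing visit is deleted. This breaks the promise to include everyone.
- **One row per visit, no subject term.** Everyone stays in, but the rows are treated as independent. The CPM comparison, which is between women, gets a standard error that is too small. The group-by-time comparison, which is within women, gets one that is too large.

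A subject effect through a RANDOM or TEST statement would be a third route, giving an approximate test. The plan does not specify it.

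At stake is the p-value for decisional regret. Two analysts could both follow section 4.0 and report different results, one of them with a false-positive rate several times the nominal level. The study hypothesises more regret after CPM and is meant to inform an irreversible choice, so a falsely significant CPM effect is the costly error.

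**Working it through.** **Inputs.** Section 4.0: two-sided 5% level; 345 enrolled, 311 continuing, 280 complete; 32 CPM and 248 non-CPM; 11.5% CPM; 10% attrition and 10% eligibility loss; r = 0.3, 0.5, 0.7. Section 3.0: m = 4 visits for decisional regret.

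**Plan's own figures.** 345 × 0.9 = 310.5 and 310.5 × 0.9 = 279.5, matching 311 and 280. For 32 vs 248 and an effect of 0.54 SD, √(1/32 + 1/248) = 0.188 and 0.54/0.188 − 1.96 = 0.915, giving power 82% against the stated 80%. These reproduce.

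**Row-per-visit layout, CPM test.** With equal correlation r, the variance of the group difference is understated by the factor DE = 1 + (m − 1)r. True size = 2 × [1 − Φ(1.96/√DE)].

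| r | DE, m = 4 | True SE / reported SE | True size, 4 visits | True size, 5 visits |
|---|---|---|---|---|
| 0.3 | 1.9 | 1.38 | 15.5% | 18.6% |
| 0.5 | 2.5 | 1.58 | 21.5% | 25.8% |
| 0.7 | 3.1 | 1.76 | 26.6% | 31.5% |

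The five-visit column applies only to outcomes also asked at baseline. Simulation with 36 vs 275 women, four visits and group, visit and group × visit terms gave 15.7%, 21.9% and 26.4% with no missing data. With 10% random dropout (assumption) it gave 15.3%, 20.0% and 25.3%.

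**Row-per-visit layout, group-by-time test.** The within-woman variance is (1 − r) times the residual variance used, so size = P(χ²₃ > 7.81/(1 − r)) = 1.1%, 0.1% and <0.1%.

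**REPEATED layout.** The sample-size paragraph can be read two ways.

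- If eligibility loss comes first, up to 311 − 280 = 31 women have incomplete data and are deleted. CPM women go from 0.115 × 311 = 35.8 to 0.115 × 280 = 32.2. The detectable visit-averaged difference at 80% power, 2.80 × √((1 + 3r)/4) × √(1/n₁ + 1/n₀), goes from 0.342/0.393/0.437 SD (36 vs 275) to 0.363/0.416/0.463 SD (32 vs 248), a ratio of 1.06.
- If attrition comes first, those 31 are eligibility losses and the documents give no count of missing forms. If 10% of forms were missing independently at each of four visits (assumption), 311 × 0.9⁴ = 204 women would remain, about 23 with CPM. At 5% and 15% missing, 253 and 162 would remain.

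A five-visit REPEATED layout, as the General text lists the visits, would leave no complete case for regret, which has no baseline score.

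**Missing-data condition.** The model in the General text contains only CPM, time and their interaction. Dropout that depends on a woman's earlier scores therefore falls outside the stated condition. The planned check could find such dropout, but this model has no means of using those scores. Observed data cannot establish whether missingness is at random, so the imputation trigger cannot be applied reliably.

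Illustration, all parameters assumed: true difference 0.54 SD; dropout logit −3.85 plus the previous score in both groups (odds × 2.7 per SD); about 85% of CPM women, 91% of others and 90% overall retained. Over r = 0.3 to 0.7 the estimated difference was 0.52–0.54 row per visit, 0.50–0.52 in complete cases, and 0.54–0.55 by generalised least squares with the true covariance, standing in for a mixed model. Simulation noise is a little under 0.01, so only the ordering and the small size should be read from this.

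**The case against.** The strongest reply is that the 16–27% depends on code that no section writes out. A reader of the whole of section 4.0 is told that scores are correlated within women and that a mixed model will be used. The three questions posed in the General text are standard repeated-measures output. The likeliest explanation may be that the wrong SAS procedure was named. The General text also calls the PROC GLM analyses initial, which could mean that the mixed model follows. On one reading of the sample-size paragraph the REPEATED layout costs only 6% in detectable difference, and the dropout bias is small.

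Much of this stands as context. The inflation is conditional on the row-per-visit layout and is not a forecast of what the analyst will do. The REPEATED cost is modest on that reading, although it would be larger if forms are missed intermittently. It is also fair that the mixed-model text gives no covariance structure or degrees-of-freedom method for the analysis itself, so it is not yet a complete specification.

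It does not remove the point. The General text calls the PROC GLM analyses primary as well as initial, and the missing-data claims refer to PROC GLM alone. Of the two standard layouts, the only one that literally keeps every woman is the one with the invalid test. If the wrong procedure was named by mistake, the text still needs correcting before analysis.

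**Conclusion.** The concern holds, and the text should be corrected before analysis. Section 4.0 gives two analyses for the primary outcome without saying which governs, and its statement about PROC GLM and missing visits is wrong for the REPEATED form. If the promise is kept by using one row per visit, the nominal 5% CPM test for decisional regret has a true size of about 16%, 22% or 27% at the plan's correlations, and the group-by-time test is far too conservative. If REPEATED is used, women are lost: up to 31 of 311 on one reading of the plan's figures, possibly more if forms are missed intermittently.

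The sizes assume equal correlation between visits and four visits per woman. The dropout parameters are illustrative; that bias is secondary to the test size.

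**What to change.** - In the General and Missing Data text, replace PROC GLM with the linear mixed model already named before Table 3, and state that it is the primary analysis. For example: PROC MIXED with REML, all available visits, group, visit and group × visit, with the within-woman covariance and the degrees-of-freedom method stated.
- Use the four post-surgery visits for decisional regret and satisfaction with decision.
- Delete the claims about PROC GLM and missing data. Restate the assumption as missing at random given observed scores and the covariates in the model.
- Run the multiple-imputation sensitivity analysis in any case, with its differing assumptions named in advance, rather than only if the data seem to require it.

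The cost is SAP wording and a few lines of SAS code, with no new data or patients.
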